5.2 Secondary Outcomes

WH 2a – We hypothesize that more pMDD patients in the placebo group will be put on antidepressant medication compared to the Omega-3 fatty acids group.

WH 2b – We hypothesize that the Omega-3 fatty acids group will achieve a higher level of functioning (a higher CGAS score) and a better quality of life (overall and within the five dimensions as assessed with KIDscreen-CAT -27) compared to the placebo group.

WH 2c – We hypothesize that the Omega-3 fatty acids group will spend fewer days in hospital and will have a lower outpatient service use (measured with the attrition check list) compared to the placebo group also resulting in a reduction in overall costs (calculated via TARMED points).

WH 2d – We hypothesize that the overall retention rate will be higher in the Omega-3 fatty acids group compared to the placebo group (or, in other words the placebo group will have more and earlier drop outs due to lack of efficacy). This hypothesis will be tested by two means: 1.) in the ITT sample independent if they received an antidepressant in the due course of the trial, as well as 2.) in a modified ITT sample, where those subjects that are put on an antidepressant will be considered as drop-outs from the day they received the first dose of an antidepressant.

WH 3a – Based on the recent meta-analysis [62] showing increased inflammatory mediators in adult MDD, we assume that at least 50% of participants will have a baseline increase of inflammatory mediators (in particular hsCRP, IL-1, IL-6) and a decrease of anti-inflammatory markers (IL-10). Based on a recent Omega-3 fatty acids treatment study in adult MDD [63], we hypothesize that Omega-3 fatty acid response will be predicted by the ratio between pro- and anti-inflammatory markers.

WH 3b – Based on the meta-analysis by Lin et al [54] as well as the study of Potalla et al [61] in pMDD, we hypothesize that about 80% of participants with pMDD will have a reduction in red blood cell Omega-3 fatty acids content, in particular EPA and DHA (used to calculate the Omega-3 index® [207, 208]). We hypothesize that those with an omega-3 index® <4 at baseline will benefit more from Omega-3 fatty acids treatment, whereas those with an omega-3 index >5 (approx. 20%) will not show a marked benefit from Omega-3 fatty acids treatment. We further hypothesize that a high n-6/n-3 Omega ratio at baseline will be associated with a better response to Omega-3 fatty acids.

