- Furthermore, we plan to reanalyze the IIT sample according to the PUFA baseline status. In particular we want to compare participants with a omega-3 index <3 compared to those with an omega-3 index $>3/5$ or 8, as increasing evidence suggest that in particular those with a low omega-3 index may benefit from omega-3 supplementation.
- Furthermore, we plan to investigate the influence of inflammatory mediators as response predictors [63].
- Finally we will reanalyze the ITT sample using compliance data (pill count, rbc EPA/DPA change levels, MARS score) to compare fully compliant study participants with partially compliant and non-compliant patients.
- More exploratory will be the analysis of EPA metabolites (HETE; E-series resolvins, prostaglandine, leukotriene) that will be measured in the context of a PhD project as potential predictors of omega-3 fatty acid response.

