11.4.3 Secondary Analyses

Important CDRS-R-related outcome measures include response and remission. Remission is defined as a CDRS total score <28 and response is defined as a 30% drop in CRDS total baseline score (post placebo lead in). Participants using additional antidepressants, days on trial before the additional antidepressant, KIDscreen-CAT-27, and DIKJ will also be analyzed. Supportive endpoints include the number of days in the hospital and the amount of outpatient service use. For analysis details related to secondary and supportive outcomes of the primary trial reporting, please see the separate Statistical Analysis Plan document.

For further secondary outcomes, we will apply the same statistical strategy as for the primary outcome measures. Analysis will include changes in overall and subscores of the in chapter 9.2 listed secondary outcome instruments. We will analyze CDRS-R subscores, DIKJ, BHS, BAI, SIQ-Jr, IES-27, KIDscreen-CAT-27, PSS-10, and Resilience Scale scores and compare them between the treatment groups.

Furthermore, we'll run the following analyses to test our secondary working hypotheses:

- **WH3a:** We will test the effect of inflammatory mediators on the efficacy of omega-3 treatment by introducing an additional continuous factor (ratio between pro- and anti-inflammatory markers) into the linear regression model described in 11.4.2.
- **WH3b:** We will calculate an omega-3 index based on red blood cell Omega-3 fatty acids content and introduce an additional binary factor (n-6/n-3 Omega ratio < 3 vs. n-6/n-3 Omega ratio > 5) into the linear regression model described in 11.4.2.
- **WH3c:** We will test whether direct metabolites of EPA are a strong predictor of Omega-3 fatty acids by introducing additional continuous factors (levels of HETEs and E-series-resolvins at baseline) into the linear regression model described in 11.4.2

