- **WH4a:** We will test association between pro-inflammatory state and depressive symptoms by calculating Pearson's correlation coefficient or Spearman's correlation coefficient between the severity of symptoms at baseline and the ratio between pro- and anti-inflammatory markers. The same procedure is also applied to omega-6/3 ratio and omega-3 index. To test whether normalization of these parameters will correlate with improvements in depression scores we'll run a linear regression model with depression scores as dependent, and time and pro-inflammatory state, increase in omega-6/3 and omega-3 index as independent variables.
- **WH4b:** We will calculate Pearson's correlation coefficient or Spearman's correlation coefficient of omega-3 index with SIQ-Jr scores depending on the distribution of the data.
- **WH4c:** As above, we will calculate either Pearson's correlation coefficient or Spearman's correlation coefficient (depending on the distribution of the data) between omega-3 index and scores on the IES-27 and overall psychopathology scores.
- **WH4d:** We also test correlations between levels of Omega-3 fatty acids with salvia cortisol, F2 isoprostanes and Connor-Davidsons Resilience Scale scores by

calculating Pearson's correlation coefficient or Spearman's correlation coefficient, respectively.

- **WH5a:** In order to compare treatment groups regarding occurrence of SUSARs, we will run a two proportions z-Test. Differences in suicidal ideation scores are tested by independent t-Test (for normal distributed data) or Mann-Whitney-U-Test (for non-normal data).

The analyses will be performed after closure of the database. The trial statisticians will perform all a-priori defined statistical analyses according to the statistical analyses plan. All other clinical outcome analyses will be declared as post-hoc analysis.

Future analysis based on the BioBank or other add on projects will be subject of an own protocol with separately formulated hypotheses that will be approved the appropriate authorities.

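### The WH3b analysis computes the omega-3 index but splits patients on the n-6/n-3 ratio instead, at cuts the hypothesis does not contain and with no treatment interaction named.

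*Protocol*

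**What the plan says.** Protocol 5.2 states WH3b in two parts. The first concerns the omega-3 index. For patients with low values the expectation is that "those with an omega-3 index® <4 at baseline will benefit more from Omega-3 fatty acids treatment". For patients at the other end of the scale the text sets a second threshold: "whereas those with an omega-3 index >5 (approx. 20%) will not show a marked benefit from Omega-3 fatty acids treatment". The second part concerns the fatty-acid ratio and gives no cut-off: "a high n-6/n-3 Omega ratio at baseline will be associated with a better response to Omega-3 fatty acids".

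Protocol 11.4.3 gives the analysis meant to test WH3b: "We will calculate an omega-3 index based on red blood cell Omega-3 fatty acids content and introduce an additional binary factor". The factor is then defined as "n-6/n-3 Omega ratio < 3 vs. n-6/n-3 Omega ratio > 5" and goes into the regression model of 11.4.2.

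Protocol 11.4.1 plans a further reanalysis by baseline fatty-acid status: "we want to compare participants with a omega-3 index <3 compared to those with an omega-3 index" above a value given as 3/5 or 8.

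SAP section 2 leaves the lipid-marker response analyses to future plans. SAP 7.1.1 nevertheless keeps one: an interaction of treatment, time and omega-3 index is added to the primary model, and the p-value for comparison with the simpler model decides whether the treatment effect is consistent.

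**The concern.** An analyst following 11.4.3 literally would compute the omega-3 index, set it aside, and test a different variable. The index part of WH3b would go untested in the one place written to test it. The ratio part would be tested at thresholds that no hypothesis supports, on a subset of patients, with a term that need not measure differential treatment benefit at all.

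With index cuts of 4 and 5 in one section, 3 and one of 3, 5 or 8 in another, and ratio cuts of 3 and 5 in a third, nobody could say afterwards which contrast had been fixed in advance. At stake is whether a claim about who responds to omega-3 could be defended as prespecified. The primary comparison of arms is not affected.

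**Working it through.** The documents give no sample size, power or error rate for WH3b, so there is no figure to reproduce. The check sets the specifications side by side.

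| Place | Variable | Cuts or form | Interaction with treatment named? |
|---|---|---|---|
| Protocol 5.2, WH3b part 1 | omega-3 index | below 4; above 5 | hypothesis only |
| Protocol 5.2, WH3b part 2 | n-6/n-3 ratio | high; no cut | hypothesis only |
| Protocol 11.4.3, WH3b | n-6/n-3 ratio (index calculated, not used) | below 3; above 5 | no |
| Protocol 11.4.1 | omega-3 index | below 3; above 3/5 or 8 | no |
| SAP 7.1.1 | omega-3 index | no cut; coding not stated | yes, with time |

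**Variable.** Part 1 is about the index, and the 11.4.3 factor is about the ratio. The factor can address part 2 only.

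**Cuts.** The values 3 and 5 are not attached to the ratio anywhere in WH3b. Of the index cuts, 11.4.1 shares at most the value 5 with 5.2, and it leaves the comparator open.

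**Gap.** The factor defines two groups, below 3 and above 5. Ratios from 3 to 5 fall in neither, and the text does not say what happens to those patients. The documents give no distribution for the ratio, so the loss is unknown. Against the target of 220, every 10 percentage points of patients in the gap is 0.10 × 220 = 22 patients.

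**Model term.** Let M be the marker. Adding M alone to the 11.4.2 model estimates how M relates to the score in both arms together. That is a prognostic question. WH3b asks whether the treatment effect changes with M, which is the treatment × M term or, for trajectories, treatment × time × M. The 11.4.3 bullet names neither. WH3a and WH3c in the same list also speak only of added factors, but they at least keep the markers continuous.

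**Index groups.** Protocol 5.2 puts about 20% above an index of 5: 0.20 × 220 = 44 patients, about 22 per arm. It gives no share between 4 and 5. A contrast by index cuts would therefore rest on a small upper group. This describes the index, not the ratio factor in 11.4.3.

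**Direction.** Protocol 5.2 (WH4a) treats a higher ratio and a lower index as going together, so a ratio above 5 marks the group poorer in omega-3. Part 2 of WH3b expects that group to benefit more, so the contrast agrees with it. Protocol 11 makes all tests two-tailed. As an illustration, data were simulated for 220 patients with an assumed 80/20 split. Swapping the labels of the two groups changed the interaction estimate from −0.442 to +0.442 and left the p-value at 0.176.

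**The case against.** The strongest reply is that the SAP already handles the main question. SAP 7.1.1 tests a treatment by time by index interaction without cuts, and the index is a covariate in the primary model. Protocol 11.4.3 ties a-priori analyses to the statistical analysis plan and adds "All other clinical outcome analyses will be declared as post-hoc analysis", so the index interaction counts as prespecified. This stands. A reader might infer that the protocol bullet is the only advance specification, or that any test on the index must be called post hoc. Neither follows.

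A reader might also infer that the ratio is simply the wrong variable, or that the test runs in the wrong direction. WH3b contains an explicit ratio hypothesis, so the ratio is a legitimate moderator. The bullet states no direction, and a ratio above 5 fits the expected responders. A reversal would arise only if 3 and 5 were index cuts carried over by mistake. That is possible, but the documents do not say so.

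It can also be said that an interaction is implied, and that the marker hypotheses are not among the SAP's confirmatory secondary endpoints. The first may be what was intended, but the text should say it. The second is correct and limits the importance of the point.

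The reply leaves gaps. SAP 7.1.1 does not mention WH3b, does not state how the index is coded, and asks only for a model-comparison p-value. That p-value cannot show whether benefit is larger below 4 or absent above 5. It does not cover the ratio, for which 11.4.3 is the only analysis described.

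**Conclusion.** The point holds as an inconsistency in the specification of a named secondary hypothesis, and it should be corrected. As written, 11.4.3 leaves the index part of WH3b untested in its own bullet. It tests the ratio part at unsupported cuts with an undefined middle group, and it does not name the interaction that a response predictor needs. Protocol 11.4.1 adds conflicting index cuts. SAP 7.1.1 covers the index question in part.

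The size cannot be put as lost power or information. Any such figure would need the distribution of the n-6/n-3 ratio, which the documents do not give, and a figure derived from the 20% above an index of 5 would describe a different split. No primary, confirmatory or safety conclusion depends on this bullet. The conclusion rests on the text alone; the only outside assumption is the 80/20 split in the simulated illustration of direction.

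**What to change.** Amend Protocol 11.4.1 and 11.4.3, or put one paragraph in the follow-up analysis plan before marker data are analysed:

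- Test the index part of WH3b with the continuous baseline omega-3 index in the SAP primary model, with its treatment × time × index interaction as in SAP 7.1.1 and the lower-order terms. State the coding.
- Report the treatment effect with a 95% confidence interval at index 4 and index 5. In the SAP's notation the 36-week effect at index x is (β1 + β11) + (θ1 + θ11)·x, where θ1 and θ11 are the added treatment × index and treatment × 36 weeks × index coefficients.
- Test the ratio part in a separate model, with the continuous n-6/n-3 ratio and the same interaction.
- Delete the ratio cuts in 11.4.3 and the index cuts in 11.4.1.

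The cost is wording. Baseline red-cell fatty acids are already part of the planned sampling, so no new data or patients are needed. The ratio analysis gains most from early timing, because it has no place in the current SAP and its a-priori status would depend on the follow-up plan.

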Outcome(s):	The German S3 Guidelines for the treatment of depression in children and youth define the background treatment for all participants. All clinical partners will be trained and monitored accordingly. The primary outcomes are the (continuous) Children's Depression Rating Scale-revised (CDRS-R) total score and the (dichotomous) rates of recovery defined by the absence of pMDD for >4months at 36 weeks, as well as response and remission rates at 12 and 36 weeks. Inflammatory mediators in serum using immunoassays, red blood cell omega-3, 6, 9 and trans fatty acids using gas chromatography (GC) and bioactive lipid mediators (e.g. E-series resolvins) using mass spectrometry (LC-MS/MS) will be measured as potential response predictors. Adverse events/ harm endpoints (in particular suicidality) will be coded using MedDRA. Adherence measurements are pill counts, as well as n-3 EPA/DHA levels across the study. Blood samples will be taken at study entry, week 12 and 36.
Study design:	A Swiss, multicentre, randomised, double-blind, placebo-controlled clinical trial.
Inclusion / Exclusion criteria:	The study aims to randomize a sample of 220 individuals aged 8 - 17 years, who are in- or outpatients of a participating centre and have a present primary diagnosis of major depression disorder with depressive symptoms of at least moderate severity. Participants with pre-existing neurological or medical conditions likely to be responsible for the depressive symptoms or other psychopathological diagnoses are excluded.
Measurements and procedures:	The study design incorporates a 1-2week screening, a 7 -10days placebo lead-in and a 36week double-blind placebo-controlled treatment phase. The severity of the depression and psychosocial functioning will be assessed at baseline and at each study visit (twice in the acute phase and twice in the maintenance phase) using a variety of different questionnaires and rating scales. Cognitive testing and biological markers (blood, urine and saliva) will be sampled at baseline and at 12 and 36 weeks. Adherence to the study will be checked by pill count at each study visit and PUFA level measurements in red blood cell membranes at baseline, 12 and 36 weeks will be performed.

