Study Product / Intervention:	In the proposed study we use for the active treatment a daily dose of 500mg EPA/ 250mg DHA in our 8 to <13 year olds, and 1000mg EPA / 500mg DHA in our 13 to <18 years olds (which corresponds with the omega-3 fatty acid doses used in adult MDD RCTs). The drug will be administered for 36 weeks.
Control Intervention (if applicable):	Placebo capsules will contain mostly medium chain triglycerides (MCT) and each capsule will also contain 1.6mg of fish oil to mimic the fishy flavour and taste.
Number of Participants with Rationale:	We aim to randomize 220 participants with at least one follow-up assessment in total, resulting in 110 participants per treatment group. Furthermore, we will recruit up to 20 additional patients to account for the number of patients who started antidepressant within the first 6 weeks of treatment. We performed a sample size calculation based on the effect size of 0.54 found in a previous meta-analysis on the effect of omega-3 fatty acids in aMDD. Sample size calculations were then adjusted for a higher placebo-response rate in minors given our multi-centre study. The analysis resulted in the inclusion of 108 patients per treatment group to achieve 80% or greater power to detect a difference of 20% in response rates between the two treatment groups. Our sample of 220 participants exceeds therefore the projected sample size needed to detect a clinical meaningful difference. A detailed explanation of the sample size calculation can be found under Section 11.2.
Study Duration:	The study duration is projected to be about four years months for patient recruitment and assessment and another year to finish up all the analysis and generate the final study report. We expect that all assessments with patients will be completed by March 2022.
Study Schedule:	First participant in: 01.03.2017 Last participant in: 31.05.2021 Last participant out: 31.03.2022 Database closure: 31.04.2022 Final analysis: 01.09.2022 Study report: 31.12.2022

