WH 3c – We hypothesize that low levels of direct metabolites of EPA, in particular HETEs and the E-series-resolvins (RvE1 & 2) will be a strong predictor of Omega-3 fatty acids response.

WH 4a – Based on the meta-analysis of Lin et al [54], we hypothesize that severity of depressive symptoms will be associated with a pro-inflammatory state, as well as an increase in omega-6/3 ratio and a decrease in omega-3 index. Normalization of these parameters will correlate with improvements in depression scores (CDRS-R, DIKJ).

WH 4b - Based on the study by Huan et al [52], we assume an inverse correlation between Omega-3 fatty acids and suicidal ideation (SIQ-Jr), in particular high levels of EPA will protect against suicidal ideation.

WH 4c – Based on the study by Beier et al [209] we assume that low Omega-3 fatty acids, in particular low EPA levels (and a low omega-3 index) will be associated with affect dysregulation, impulsivity/ emotionality (IES-27) and overall psychopathology.

WH 4d – Based on Kiecolt-Glaser et al [205], we hypothesize that high levels of overall stress (as measured with the PSS scale) will correlate with low levels of Omega-3 fatty acids, a pro-inflammatory state, increased saliva cortisol, and high levels of PUFAs oxidation products as

measured by F2 Isoprostanes in the urine and be inversely correlated with the Conner-Davidsons Resilience Scale.

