9.2.4.2 Laboratory Parameters

At screening and at nine months (or the drop out visit), blood will be drawn for standard clinical laboratory tests. Clinical blood parameters (haemoglobin, haematocrit, leucocytes, thrombocytes, TSH (thyroid function test), ALAT & ASAT (liver function test), and thromboplastin (blood coagulation) will be assessed in order to screen the patient for abnormal blood parameters. These analyses will be done in the Children's hospital of Zurich. The results will be entered into the eCRF as they are part of the inclusion criteria and will also provide the stratification parameter (hSRF). All the other blood samples will be stored for analyses as outlined in the protocol.

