11 STATISTICAL METHODS

Descriptive statistics will be provided for all data broken down by medication (omega-3 fatty acids and placebo), group (patients who recovered from the depression, patients who did not recover) and visit. Mean, median, standard deviation, range and number of observations will describe continuous variables. Frequencies and percentages will describe discrete variables. All statistical tests will be carried out two-tailed; the alpha (level of significance) is 5%. Efficacy of the treatment will be assessed using a linear random coefficient regression model.

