11.4.2 Primary Analysis

The continuous primary outcome measure is the CDRS-R total score. We will analyze the primary efficacy measure using a joint model containing a linear random effects regression model (similar to the TADS study [253, 254]) and a time-to-event model to account for missing information due to additional antidepressant use. Random regression in an ITT sample permits estimation of changes in continuous repeated measures in the presence of missing data on both a population and participant-specific level without necessitating last observation carried forward or exclusion of participants because of missing data. We will model the impact of treatment on outcome as a linear function of fixed effects for treatment, time (defined as the natural log of days since baseline + 1) and treatment-by-time interaction and random effects for participant and clinical site. Under the assumption of random intercepts and slopes for each patient, the overall and treatment group-specific rate of change for the 2 treatment groups for the primary CDRS-R outcome will be examined. A comparison on treatment slopes (linear trends with time) will then be conducted.

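### The WH4a regression of depression scores on time and markers names no patient term, does not isolate within-patient change, and leaves out treatment arm

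*Protocol*

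**What the plan says.** Protocol 5.2 (WH 4a) predicts that as the inflammatory state, omega-6/3 ratio and omega-3 index normalise, depression scores improve. Protocol 11.4.3 gives the test. "To test whether normalization of these parameters will correlate with improvements in depression scores", the team will "run a linear regression model with depression scores as dependent, and time and pro-inflammatory state, increase in omega-6/3 and omega-3 index as independent variables". No participant, site or treatment term is listed, and the visits that enter are not named.

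Three other places bear on how to read this:

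- The synopsis gives the sampling times: "Blood samples will be taken at study entry, week 12 and 36".
- Protocol 11.4.2 specifies participant and site random effects for the primary outcome ("Under the assumption of random intercepts and slopes for each patient"). WH3a, WH3b and WH3c each refer to that model. WH4a does not.
- The SAP (Section 2, scope) reserves the relationships between markers and symptoms for follow-up analyses under future plans. It contains no WH4a model, so 11.4.3 is the only specification on paper.

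**The concern.** Time as a regressor, with bloods at three visits, implies several rows per patient. A regression that treats those rows as independent understates the standard error whenever marker and score both persist within a patient, as trait-like measures tend to do.

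Two further problems concern what is estimated rather than its precision.

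- **Level against change.** The hypothesis relates change to change. The model has the score level as outcome and at least one marker as a level. A patient whose index is always low and whose score is always high would count as evidence that normalisation goes with improvement.
- **Arm.** Active capsules carry about 168 mg EPA and 84 mg DHA each, and placebo about 1.6 mg of fish oil (Protocol 8.1.1, 8.1.2). The index should therefore move mainly in one arm. If treatment also lowers scores by any route, the marker coefficient picks up the arm difference.

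At stake is a biomarker claim reported with intervals that are too narrow and an interpretation that the model does not support.

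**Working it through.** **Inputs**

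- Nominal level: two-sided 5% (Protocol 11).
- Patients: 220 (synopsis). The large-sample error rate hardly depends on this.
- Visits with markers and score: m = 3 (synopsis). For hsCRP m could be 2. Protocol 9.2.2.4 lists hsCRP at enrolment, week 12 and week 36, but 9.2.4.2 says "At screening and at nine months (or the drop out visit), blood will be drawn for standard clinical laboratory tests".
- Within-patient correlations of marker (ρx) and score (ρy): not given anywhere, so assumed from 0.3 to 0.8.

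The documents state no error rate for WH4a beyond the nominal 5%, so there is no figure to reproduce. With ρx = 0 the formula below returns 5.0%, as it should.

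**Clustering**

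Variance ratio DE = 1 + (m − 1)·ρx·ρy. Actual level = 2·[1 − Φ(1.96/√DE)]. Shortfall of the standard error = 1 − 1/√DE. The last column is a simulation of ordinary least squares with three markers, time as a factor and no true association, giving the range over the markers.

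| ρx = ρy | DE (m = 3) | Actual level | SE too small by | Simulated level |
|---|---|---|---|---|
| 0.3 | 1 + 2(0.09) = 1.18 | 7.1% | 8% | 6.5–6.9% |
| 0.5 | 1 + 2(0.25) = 1.50 | 11.0% | 18% | 9.8–10.8% |
| 0.6 | 1 + 2(0.36) = 1.72 | 13.5% | 24% | 13.1–14.3% |
| 0.7 | 1 + 2(0.49) = 1.98 | 16.4% | 29% | 14.9–17.5% |
| 0.8 | 1 + 2(0.64) = 2.28 | 19.4% | 34% | 18.7–20.5% |

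Other readings:

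- Two visits: DE = 1 + 0.25 = 1.25 gives 8.0% at correlations of 0.5. DE = 1 + 0.49 = 1.49 gives 10.8% at 0.7.
- All markers entered as change from baseline: about 8% to 10% in simulation at 0.5 to 0.7.
- Only the omega-6/3 ratio entered as change: about 8% for that term, and 8% to 11% if treatment also shifts the marker by 2 SD.

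A patient random intercept brings the simulated level back to about 4% to 6%. Cluster-robust errors give about 4% to 6.5%.

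**Arm**

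A marker shift in one arm with no treatment effect on the score hardly alters the rates above. The problem appears when both move. A simulation took no marker–score link within arm, a treatment effect of 0.4 SD (the SAP 6.1 conservative planning value) and an assumed marker shift of 1 or 2 SD in the active arm. The pooled regression without arm rejected in about 37% and 71% to 73% of runs. Cluster-robust errors without arm still rejected in about 22% to 26% and 53% to 59%. Adding arm and arm-by-time returned 4% to 6%.

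**Level against change**

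With an assumed correlation of −0.2 between patients' stable marker and score levels, and no within-patient link, the pooled regression rejected in 69% to 89% of runs. It detects a real association between patients, but not the one that WH4a is about.

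**The case against.** Several points on the other side are fair.

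- **Ordinary, stacked regression is an inference.** 11.4.3 does not say ordinary or pooled, and WH3a-c call the 11.4.2 mixed model a linear regression model too. That stands as a limit on certainty. The missing cross-reference in WH4a, directly after three hypotheses that have one, still makes ordinary regression the more natural reading.
- **11.4.3 promises the primary strategy for further secondary outcomes.** That sentence leads into rating scales compared between arms. The working-hypothesis tests are then introduced separately with their own methods, so it does not settle WH4a.
- **The SAP defers the analysis.** True, and no WH4a p-value has been fixed. But deferral without a replacement leaves the 11.4.3 text as the default.
- **The word increase may govern the omega-3 index as well as the omega-6/3 ratio.** That is possible. Two of three markers would then be change terms, and the lower range of about 8% to 10% would be the closer guide for them. The inflammatory term and the outcome would still be levels.
- **Leaving out arm can be deliberate.** WH4a does not say within arm, and treatment-driven change may be part of the association of interest. This stands: the choice needs stating, and both estimates can be reported.
- **Data may be thinner than three rows each.** Bloods beyond the initial laboratory sample are optional (Protocol 9.2.2.4), which lowers the effective m.

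A reader might infer that the plan carries a fixed false-positive rate of, say, 11% to 16%. The documents do not support that. Those values belong to assumed correlations of 0.5 to 0.7 at three visits. A reader might also infer that the missing arm term is what makes the standard errors too small. It is not: it causes confounding, and the missing patient term causes the small standard errors.

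**Conclusion.** The point holds conditionally. Followed literally on repeated visits, the WH4a model understates its standard errors. A nominal 5% test then rejects in about 7% to 20% of null cases at three visits, for assumed correlations of 0.3 to 0.8 in both marker and score. At correlations of about 0.5 to 0.7, two visits or change-score markers give about 8% to 11%. If the marker does not persist within patients there is no inflation.

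Independently of the standard errors, the model does not isolate the change-with-change association in the hypothesis. Without arm, it also cannot tell a marker association from the randomised contrast. The size of these two effects depends on assumed shifts and correlations, so the simulated figures are illustrations.

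WH4a is a secondary hypothesis that the SAP has set aside for later. No primary or confirmatory conclusion depends on it.

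**What to change.** In Protocol 11.4.3 or, more simply, in the follow-up analysis plan that the SAP foresees:

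1. State which visits enter WH4a, and reconcile the hsCRP sampling times in 9.2.2.4 and 9.2.4.2.
2. Use a mixed model of the 11.4.2 type with at least a patient random intercept and a site effect, or cluster-robust errors.
3. Enter each marker as its baseline value and its change from baseline, and name the change coefficient as the WH4a test. The mixed model is preferable here. When a marker fluctuates between visits, a later value still says something about the patient's stable level even given the baseline value, and a pooled fit with robust errors gives that more weight.
4. Include arm and arm-by-time. Report the estimate without arm alongside if the total association is also of interest, labelled as such.

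The cost is a few sentences and wider intervals. No extra data are needed.

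Random slopes and separate within-arm estimates are optional. They are not needed to restore the nominal level.
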